4.5.2.2 Physical and Obstetric Examinations

A complete physical examination in women should include measurement of height and weight, an evaluation of head, eye, ear, nose, and throat, cardiovascular, dermatological, musculoskeletal, respiratory, and gastrointestinal systems, as well as vital signs (see following section). To reduce the burden of visits on the mothers, results from physical examinations done as part of routine care may be used. The following assessments will also be conducted: neurological examination (see Section 4.5.2.4), relapse description, and EDSS (see Section 4.5.2.6). Changes from baseline abnormalities should be recorded in patient notes. New or worsened clinically significant abnormalities not related to MS should be recorded as adverse events on the Adverse Event eCRF. Height will be measured at screening only.

An obstetric examination will be performed as per local clinical practice, at visits indicated in Appendix 1 (Schedule of Assessments). To reduce the burden of visits on the mothers, results from obstetric examinations done as part of routine care may be used.

See Appendix 1 (Schedule of Assessments) for the timing of all assessments.

4.5.2.3 Vital Signs

Vital signs may be measured, in particular throughout the infusion procedure as per the Label and may include measurements of heart rate, systolic and diastolic blood pressures, and temperature. If those measurements are performed as per clinical practice and are available, record any abnormalities observed on the General Medical History and Baseline Conditions eCRF. At subsequent visits, record new or worsened clinically significant abnormalities on the Adverse Event section of the eCRF (as presented in Section 5.1.2).

4.5.2.4 Neurological Examination

A neurological examination will be performed at every planned visit and at unscheduled visit if applicable. To reduce the burden of visits on the mothers, results from neurological examinations done as part of routine care may be used. For women referred to the investigator, results from routine visits at the woman's neurologist may be

used. In the presence of newly identified or worsening neurological symptoms at any given time in the study, a neurological evaluation should be scheduled promptly.

As infection is a potentially serious complication of B-cell-depleting therapy, investigators will also screen women for signs and symptoms of any CNS infections, and specifically progressive multifocal leukoencephalopathy (PML), by evaluating neurological deficits localized to the cerebral cortex, such as cortical symptoms/signs, behavioral and neuropsychological alteration, retrochiasmal visual defects, hemiparesis, cerebellar symptoms/signs (e.g., gait abnormalities, limb incoordination). Women with suspected PML should be withheld from ocrelizumab treatment until PML is ruled out by complete clinical evaluation and appropriate diagnostic testing. A woman with confirmed PML should be withdrawn from the study. PML should be reported as a serious adverse event (SAE; with all available information) with immediate notification of the Medical Monitor. Refer to Appendix 3 for guidance for diagnosis of PML.

4.5.2.5 Assessment of Relapses

Potential relapses should be recorded throughout the study period after screening. See Appendix 1 (Schedule of Assessments) for the timing of these assessments.

All new or worsening neurological events consistent with MS representing a "clinical relapse" are to be reported on the dedicated "MS relapse" form. A clinical relapse is defined as a monophasic clinical episode with patient-reported symptoms and objective findings typical of MS, reflecting a focal or multifocal inflammatory demyelinating event in the CNS, developing acutely or sub-acutely, with a duration of at least 24 h, with or without recovery, and in the absence of fever or infection (Thompson et al. 2018). Multiple sclerosis relapses should not be reported as an AE, unless they are serious.

It is recommended that women with new neurological symptoms suggestive of a relapse have an EDSS/Functional Systems Scores (FSS) assessment performed as soon as possible, ideally within 7 days of the onset of symptoms. However, it is not mandatory to perform an EDSS assessment in case of a suspected relapse.

4.5.2.6 Assessment of Disability

Disability in MS will be measured by the EDSS. See Appendix 1 (Schedule of Assessments) for the timing of assessments.

The EDSS is based on a standard neurological examination, incorporating seven functional systems (pyramidal, cerebellar, brainstem, sensory, bowel and bladder, visual, and cerebral [or mental], plus "other") rated and scored as FSSs. Each FSS is an ordinal clinical rating scale ranging from 0 to 5 or 6. These ratings are then used in conjunction with observations and information concerning ambulation and use of assistive devices to determine the EDSS score. The EDSS is a disability scale that ranges in 0.5-point steps from 0 (normal) to 10 (death) (see Appendix 4). *The EDSS*

assessment may also be performed by the investigator via telephone, using a specific licensed questionnaire (see Appendix A4–2).

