	• Note: Immune responses to the following may be included: measles, mumps, rubella, tetanus , diphtheria, pertussis, varicella zoster, Streptococcus pneumoniae , HBV, and SARS-CoV-2; along with nucleocapsid and spike protein titers; only for those mothers who have received the vaccine, as per local clinical practice)
 To measure disease activity in mothers during pregnancy and postpartum 	 Number of MS relapses during pregnancy and postpartum (clinical relapses)
	 Mean change from baseline in the EDSS score over the course of the study
 To detect presence of neuroaxonal damage in the mother during pregnancy and postpartum 	• sNfL levels during pregnancy (second trimester [time frame of blood sampling: Week 24–30], third trimester [time frame of blood sampling: Week 35] and at delivery [time frame of blood sampling: within 24 hours after delivery]) and postpartum (in line with ocrelizumab administration timepoints)

Table 1 Objectives and Corresponding Endpoints (cont.)

ASQ-3 = Ages and Stages Questionnaire, version 3; EDSS = Expanded Disability Status Scale; HBV = hepatitis B virus; Hib = Hemophilus influenzae type b; LLN = lower limit of normal; MMR = measles, mumps, and rubella; MS = multiple sclerosis; PCV-13 = 13-pneumococcal conjugate vaccine; SARS-CoV-2 = severe acute respiratory syndrome coronavirus 2; sNfl = serum neurofilament light chain; WHO = World Health Organization.

Table 1 Objectives and Corresponding Endpoints (cont.)

Objectives	Corresponding Endpoints
Exploratory Objectives (cont.)	
 To evaluate the evolution of B-cell levels between birth and the first year of life 	 Trajectory (absolute and percentage changes) of B-cell (CD19 + cell) levels in the infant from Week 6 of life to 1 month after the first or second dose of MMR vaccine or Month 13 of age in case MMR vaccine is not planned to be administered

ASQ-3=Ages and Stages Questionnaire, version 3; EDSS=Expanded Disability Status Scale; HBV=hepatitis B virus; Hib=Hemophilus influenzae type b; LLN=lower limit of normal; MMR=measles, mumps, and rubella; MS=multiple sclerosis; PCV-13=13-pneumococcal conjugate vaccine; SARS-CoV-2=severe acute respiratory syndrome coronavirus 2; sNfl=serum neurofilament light chain; WHO=World Health Organization.

3. STUDY DESIGN

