3. PYRAMIDAL FSS

0	normal
1	abnormal signs without disability
2	minimal disability: patient complains of motor-fatigability or reduced performance in strenuous motor tasks (motor performance Grade 1) and/or BMRC Grade 4 in one or two muscle groups
3	mild to moderate paraparesis or hemiparesis: BMRC Grade 4 in > two muscle groups; and/or BMRC Grade 3 in one or two muscle groups (movements against gravity are possible); and/or Severe monoparesis: BMRC Grade 2 or less in one muscle group
4	marked paraparesis or hemiparesis: usually BMRC Grade 2 in two limbs and/or monoplegia: BMRC Grade 0 or 1 in one limb; and/or moderate tetraparesis: BMRC Grade 3 in \geq three limbs
5	paraplegia: BMRC Grade 0 or 1 in all muscle groups of the lower limbs; and/or marked tetraparesis: BMRC Grade 2 or less in ≥ three limbs; and/or hemiplegia
6	tetraplegia: BMRC Grade 0 or 1 in all muscle groups of the upper and lower limbs

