Appendix 4: Expanded Disability Status Scale (EDSS)

5	Ambulatory < 100 meters without help or assistance (EDSS 6.0)
6	Ambulatory \geq 50 meters with unilateral assistance (EDSS 6.0)
7	Ambulatory \geq 120 meters with bilateral assistance (EDSS 6.0)
8	Ambulatory < 50 meters with unilateral assistance (EDSS 6.5)
9	Ambulatory \geq 5 meters, but < 120 meters with bilateral assistance, (EDSS 6.5)
10	Uses wheelchair without help; unable to walk 5 meters even with aid, essentially restricted to wheelchair; wheels self and transfers alone; up and about in wheelchair some 12 hours a day (EDSS 7.0)
11	Uses wheelchair with help; unable to take more than a few steps; restricted to wheelchair; may need some help in transferring and in wheeling self (EDSS 7.5)
12	essentially restricted to bed or chair or perambulated in wheelchair, but out of bed most of day; retains many self-care functions; generally has effective use of arms (EDSS 8.0)

Standardized Neurological Examination and Assessment of Kurtzke's Functional Systems and Expanded Disability Status Scale

Slightly modified from Kurtzke JF. Rating neurologic impairment in multiple sclerosis: an expanded disability status scale (EDSS). Neurology 1983:33,1444–52.

[©]2011 [name], Neurology, University Hospital Basel, 4031 Basel, Switzerland; Version 04/10.2

A4-2 EDSS BY TELEPHONE

- University Hospital Basel

EDSS BY PHONE

The purpose of this interview is to obtain the best possible estimate of the Expanded Disability Status Scale (EDSS) score of patients who exceptionally cannot come to the study centre and be examined by a neurologist. The current version is using the Neurostatus definitions version 04/10.2 but is fully compatible with previous versions. Ideally the same EDSS physician who assessed the patient at the last visit should do the standardized interview for EDSS by phone. The interview should be done with the patient himself. If the patient cannot be interviewed due his health condition, the interview may be done with a caregiver or his or her physician.

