When touching your face, has your sensation changed recently?

- 0 = no, normal sensation
- 2 = yes, numbness when touching some parts of the face
- 3 = yes, clearly decreased sensation in parts of the face, or pain attacks in the face
- 4 = yes, touch is not felt at all, in the complete left face, right face or both sides

When laughing or frowning your eyebrows, is your face symmetric and could you close both eyes completely?

0 = yes

- 2 = no, slight asymmetric only when laughing or frowning eyebrows
- 3 = no, asymmetric face also at rest, closure of one eye slightly impaired
- 4 = no, lid closure of one or both eyes impossible, difficulty with liquids

Do you have problems with hearing?

0 = no

- 2 = yes, slightly decreased hearing on one side
- 3 = yes, does not hear finger rub in one or both ears
- 4 = yes, deaf

Can you speak clearly?

0 = yes

- 2 = no, some difficulties in speaking, realized by others when talking with the patient
- 3 = no, dysarthria impairs conversation
- 4 = no, incomprehensible speech
- 5 = no, inability to speak

EDSS by Phone; version 1.1 - September 2019

Ocrelizumab—F. Hoffmann-La Roche Ltd 119/Protocol MN42988, Version 3

Do you have difficulties with swallowing?

0 = no

- 2 = yes, difficulty with thin liquids
- 3 = yes, difficulty with thin liquids and solid food
- 4 = yes, requires pureed diet
- 5 = yes, inability to swallow

Please take the worse single score to define the FS!

Brainstem-FS =

Pyramidal FS

Do you have had problems moving one or both arms? (no problems with your legs)

0 = no

2 = yes, one arm cannot be elevated above horizontal

- 3 = yes, almost no function of one arm
- 4 = yes, complete loss of function of one arm

Do you have problems moving one or both of your legs? (no problems with your arms)

0 = no

- 2 = yes, one leg cannot be elevated when in supine position
- 3 = yes, almost no function of one leg or mild to moderate paraparesis
- 4 = yes, complete loss of function of one leg or marked parapareris
- 5 = yes, paraplegia

Do you have problems moving your legs as well as your arms?

0 = no

- 3 = yes, mild weakness of one body half
- 4 = yes, almost no function of one body half (arm and leg) or moderate quadriparesis
- 5 = yes, complete loss of function of one body half (arm and leg) or marked quadriparesis)
- 6 = yes, quadriplegia

Please take the worse single score to define the FS!

Pyramidal-FS =

Cerebellar FS

Do you have any tremor or clumsy movements?

0 = no

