 - Number of relapses before, during pregnancy (defined by LMP) and after pregnancy (defined as after birth) will be summarized in 3-month interval respectively.
 - Number and percentage of women in each category (0, 1, 2, 3 and ≥4) in
 3-month intervals of before/during/after pregnancy.
 - Number of relapses after first OCR and up to 1 year before pregnancy, during pregnancy, up to 1 year after delivery will be presented. Annualized relapse

rate and 95% CI may also be presented if warranted by the number of data points.

- Mean EDSS score in 3-month interval of before/during/after pregnancy. In case of multiple EDSS score at the same visit, the median will be used.
- Change from baseline in EDSS by visit.
- Presence of any clinically significant abnormalities from the neurological examination (Yes, No) by visit
- Type of neurological abnormality (disability progression independent of relapse, MS relapse, signs or symptoms suggestive of Progressive Multifocal Leukoencephalopathy, Other) by visit

MS relapses, EDSS and neurological examination findings will also be listed. Analysis will also be presented for subgroups based on OCR exposure prior to the study as list in Section 4.5.4.

4.6.5 Women's Neuroaxonal Damage

To detect presence of neuroaxonal damage in the mother during pregnancy and postpartum, serum neurofilament light chain (sNfL) levels are measured at baseline (gestational age Week 24-30), gestational age Week 35, at delivery and postpartum (in line with ocrelizumab administration timepoints). Absolute sNfL levels will be log (base 10) transformed. The geometric mean with corresponding 95% CI and change from baseline will be back transformed and presented. Absolute sNfL levels as well as change from baseline based on log back transformed may also be displayed graphically over time, as appropriate.

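### EDSS by telephone cannot score grade 1 in six of seven functional systems, and the SAP has no rule for mode, so a switch of mode can record false EDSS change

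*Protocol*

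**What the plan says.** Protocol 4.5.2.6 describes the EDSS as an examination-based score: "The EDSS is based on a standard neurological examination, incorporating seven functional systems". It then adds that the "assessment may also be performed by the investigator via telephone, using a specific licensed questionnaire", and points to Appendix A4-2. That section does not limit the visits at which the telephone may be used, and it does not require the same mode at baseline and follow-up. The form in Appendix A4-2 states a narrower purpose, for "patients who exceptionally cannot come to the study centre and be examined by a neurologist".

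The endpoint in Protocol Section 2 is exploratory: "Mean change from baseline in the EDSS score over the course of the study". SAP 4.6.4 (Women's Disease Activity) plans the mean EDSS in 3-month intervals and "Change from baseline in EDSS by visit". It also says: "In case of multiple EDSS score at the same visit, the median will be used". None of these rules mentions mode of assessment.

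**The concern.** A change score is interpretable only if both measurements could have produced the same value in a woman whose condition is unchanged. At the low end of the EDSS that fails when one score comes from an examination and the other from the telephone form. The in-person pyramidal scale, for example, gives grade 1 for "abnormal signs without disability". The first non-zero answer to the telephone pyramidal question about the arms is "2 = yes, one arm cannot be elevated above horizontal". Nothing lies between that and 0.

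What is at stake is whether the change-from-baseline summary can be read as disease activity. With about 33 women planned, a few switches of mode could move a visit mean. Without a recorded mode, nobody could tell that movement from real change.

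**Working it through.** The plan gives no figure for this point, so there is none to reproduce. The check compares the two scoring forms in Protocol Appendix 4 and follows the EDSS steps in A4-1.

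**Step 1: grades available**

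| Functional system | Grade 1 in person | Telephone options (A4-2) |
|---|---|---|
| Visual | yes | 0, 1, 2, 3, 4 |
| Brainstem | yes | 0, 2, 3, 4, 5 |
| Pyramidal | yes | 0, 2, 3, 4, 5, 6 |
| Cerebellar | yes | 0, 2, 3, 4, 5 |
| Sensory | yes | 0, 2, 3, 4, 5, 6 |
| Bowel and bladder | yes | 0, 2, 3, 4, 5 |
| Cerebral | yes | 0, 2, 3, 4, 5 |

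Six of seven systems have no telephone grade 1.

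**Step 2: what EDSS 1.0 and 1.5 need.** By A4-1, EDSS 1.0 is one system at grade 1 and EDSS 1.5 is more than one. EDSS 2.0 is one system at grade 2, and 2.5 is two systems at grade 2. For women who walk at least 500 m, A4-2 takes the EDSS straight from the combination of system scores. With only one system able to score 1, telephone EDSS 1.5 is impossible, and 1.0 needs visual grade 1 with every other system at 0.

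**Step 3: in-person profiles.** With grades 0 and 1 only, there are 2^7 = 128 profiles.
- EDSS 0: 1 profile.
- EDSS 1.0: 7 profiles.
- EDSS 1.5: 128 - 1 - 7 = 120 profiles. Of these, 2^6 - 1 = 63 include visual grade 1 and 2^6 - 1 - 6 = 57 do not (63 + 57 = 120).

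These count combinations and say nothing about how common each one is.

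**Step 4: rescoring by telephone with no true change.** Visual grade 1 is kept, and each non-visual grade 1 becomes 0 or 2, the two nearest options.

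| In-person EDSS | Profiles | Telephone EDSS if rescored to 0 | If one system is rescored to 2 |
|---|---|---|---|
| 1.0, visual | 1 of 7 | 1.0 (no change) | not applicable |
| 1.0, non-visual | 6 of 7 | 0 (-1.0) | 2.0 (+1.0) |
| 1.5, no visual grade 1 | 57 of 120 | 0 (-1.5) | 2.0 (+0.5) |
| 1.5, with visual grade 1 | 63 of 120 | 1.0 (-0.5) | 2.0 (+0.5) |

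If two non-visual systems both become 2, EDSS 1.5 becomes 2.5 (+1.0). Profiles with more grade 1 systems could rise further. None of the 120 profiles keeps 1.5, and 1 of 7 keeps 1.0.

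**Step 5: direction.** Telephone grade 2 is worded more strictly than in-person grade 1. The pyramidal contrast is quoted above. For bowel and bladder, in-person grade 1 is mild and telephone grade 2 is moderate. Answered as worded, most grade 1 findings would go to 0, so the downward column is the likelier one.

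**Step 6: same-visit median.** An in-person 1.5 and a telephone 0 at one visit give (1.5 + 0)/2 = 0.75, which is not a step on a scale that moves in halves.

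**Step 7: group mean.** False shift = share of women at the visit who were at 1.0-1.5 and switched mode, times the per-woman shift. The documents give no share, so 10%, 25% and 50% are assumptions. The limits assume that all shifts go one way and use -1.5 and +1.0 per woman.
- 10%: 0.10 x -1.5 = -0.15, to 0.10 x 1.0 = +0.10.
- 25%: 0.25 x -1.5 = -0.38, to 0.25 x 1.0 = +0.25.
- 50%: 0.50 x -1.5 = -0.75, to 0.50 x 1.0 = +0.50.

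One woman in 33 shifting by -1.5 moves the mean by -1.5/33 = -0.045.

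**The case against.** The best defence is that telephone scoring will be rare and anchored. Section 4.5.2.6 refers to Appendix A4-2, whose purpose statement treats telephone use as exceptional. The form prefers the physician who did the last assessment, lets questions be adapted to known disability, says questions exploring scores below the last known EDSS may be superfluous, and relies on the Neurostatus definitions. An assessor who knows the last score was 1.5 may hesitate to record 0. This could reduce the effect, but it adds no grade 1 option. Several in-person grade 1 findings, such as signs without disability or vibration loss, need an examination.

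Three stronger readings are tempting, and the documents do not support them.
- A reader might infer that telephone scoring will cluster after birth and so mimic a pregnancy-to-postpartum change. Scheduled postpartum EDSS falls at the two infusion visits, which women attend for treatment. The Week 6 visit and the 3-monthly telephone interviews carry no EDSS, and women who switch or stop disease-modifying therapy after birth have no further maternal clinical assessments. The scheduled EDSS visit expressly allowed by telephone is early discontinuation.
- A reader might infer that women will cross the SAP's EDSS categories. The cut at 2 applies to the last scores before LMP and before enrollment, and the cut at 2.5 to baseline (SAP 4.3.1). A later telephone score cannot move anyone across either.
- A reader might treat false worsening as being as likely as false improvement. The stricter telephone wording points the other way.

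Two further points stand. Pooling of modes is inferred from the SAP's silence, and the eCRF is not among the documents, so mode may already be captured.

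**Conclusion.** The point holds as a minor one. Followed as written, the plan can record EDSS change that comes only from the form, in women at 1.0 or 1.5 whose mode differs between the scores being compared. The likely error is false improvement: -1.0 from a non-visual 1.0, -1.5 from a 1.5 without visual grade 1, and -0.5 from a 1.5 with it. An isolated visual 1.0 is unaffected, and so is a comparison of telephone with telephone when the answers are unchanged.

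This assumes that visual grade 1 survives the telephone form and that each non-visual grade 1 goes to 0 or 2. The size in the trial cannot be stated; the group-mean ranges above only show what assumed shares would produce. The endpoint is exploratory and descriptive, individual EDSS values are listed, and the primary B-cell analysis is not affected.

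**What to change.** Record the mode with each EDSS, or confirm that the eCRF already captures it. In SAP 4.6.4:
- report the number of telephone scores at each visit;
- where both modes exist at one visit, use the in-person score in place of the median;
- keep the all-scores summary of change from baseline, and beside it add one restricted to women with in-person scores at both baseline and that visit.

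The SAP already takes this kind of care in Section 4.6.2: wrong ASQ-3 questionnaires stay out of the main analysis and enter a sensitivity analysis if more than 20% of infants are involved.

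I would not drop telephone scores from the only main summary, which trades data for comparability in a small study. Nor would I recode in-person grade 1 to 0, since nothing in the documents validates that bridge.

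The cost is at most one eCRF field, a few sentences and one extra table. The restricted summary will rest on fewer scores.

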4.5.2.7 Laboratory, Biomarker, and Other Biological Samples

Routine laboratory assessments (performed in the central laboratory, except for urinalysis) are listed in the following sections. For sampling procedures, storage conditions, and shipment instructions, see the laboratory manual. For details, refer to Schedule of Assessments, Appendix 1.

At Screening/Baseline (Gestational Weeks 24-30)

- **Hematology** (hemoglobin, hematocrit, quantitative platelet count, RBC count, WBC count, absolute or/and differential count [neutrophils, eosinophils, lymphocytes, monocytes, basophils]).
- **Serum chemistries** (AST, ALT, gamma-glutamyl transpeptidase [GGT], total bilirubin, creatinine, random glucose, potassium, sodium, chloride). The scheduled obstetric blood glucose test should preferably be conducted at the screening/baseline visit (Week 24–30) rather than at a separate visit.
- **Urinalysis:** using urine dipstick at site (may include pH, specific gravity, glucose, protein, ketones, blood), and microscopic examination (sediment, RBCs, WBCs, casts, crystals, epithelial cells, bacteria) at the discretion of the investigator.
- **Hepatitis B virus serology:** Women with positive screening tests for HBV, determined by a positive HBsAg result (current infection) or positive HBcAb titers (previous infection) will be excluded. Women with documented history of HBV vaccination or positive HBsAb titers are eligible.
- **Lymphocyte subtypes:** Blood samples will be collected to measure B-cell counts (CD19 + and B-cell subsets [Table 2]), T-cell counts (CD3+, CD4+, CD8+), and natural killer (NK) cell counts (CD16+CD56+).
- Serum immunoglobulin concentration.
- **Ocrelizumab concentration:** serum samples will be collected for determination of ocrelizumab concentration.
- **sNfL:** samples will be collected for determination of sNfL.

During Third Trimester (Gestational Week 35±14 days)

Note: Samples may be collected by home nurse visit.

- **Hematology** (hemoglobin, hematocrit, quantitative platelet count, RBC count, WBC count, absolute or/and differential count [neutrophils, eosinophils, lymphocytes, monocytes, basophils]).
- **Serum chemistries** (AST, ALT, GGT, total bilirubin, creatinine, random glucose, potassium, sodium, chloride).
- **Urinalysis**: using urine dipstick at site (may include pH, specific gravity, glucose, protein, ketones, and blood), and microscopic examination (sediment, RBCs, WBCs, casts, crystals, epithelial cells, bacteria) at the discretion of the investigator.

Ocrelizumab—F. Hoffmann-La Roche Ltd

- **Lymphocyte subtypes**: Blood samples will be collected to measure B-cell counts (CD19+ and B-cell subsets [Table 2]), T-cell counts (CD3+, CD4+, CD8+), and NK cell counts (CD16+CD56+).
- Serum antibody (IgG) titers to immunizations: for measles, mumps, rubella, *tetanus*, diphtheria, pertussis, varicella zoster, Streptococcus pneumoniae, HBV and SARS-CoV-2 (along with nucleocapsid and spike protein titers; only for those mothers who have received the vaccine, as per local clinical practice) will be performed. Any vaccinations received by mothers during the study will be recorded as concomitant medications.
- **Ocrelizumab concentration:** serum samples will be collected for determination of ocrelizumab concentration.
- Serum immunoglobulin concentration.
- **sNfL:** samples will be collected for determination of sNfL.

At Delivery (within 24 hours after delivery, only for live births)

- **Ocrelizumab concentration:** serum samples will be collected for determination of ocrelizumab concentration.
- Serum immunoglobulin concentration.
- **sNfL:** samples will be collected for determination of sNfL.

During the Vaccination Period (at Infusion 1 and Infusion 2)

- **Hematology** (hemoglobin, hematocrit, quantitative platelet count, RBC count, WBC count, absolute or/and differential count [neutrophils, eosinophils, lymphocytes, monocytes, basophils]).
- **Serum chemistries** (AST, ALT, GGT, total bilirubin, creatinine, random glucose, potassium, sodium, chloride).
- **Urinalysis:** using urine dipstick at site (may include pH, specific gravity, glucose, protein, ketones, and blood), and microscopic examination (sediment, RBCs, WBCs, casts, crystals, epithelial cells, bacteria) at the discretion of the investigator.
- **Lymphocyte subtypes:** Blood samples will be collected to measure B-cell counts (CD19+ and B-cell subsets [Table 2]), T-cell counts (CD3 +, CD4 +, CD8+), and *NK cell counts (CD16+CD56+)*. Samples will be collected prior to the ocrelizumab infusion.
- **Ocrelizumab concentration:** serum samples will be collected (before ocrelizumab administration) for determination of ocrelizumab concentration
- Serum immunoglobulin concentration
- **sNfL:** On the day of the infusion, samples should be collected 5–30 minutes prior to the methylprednisolone infusion as it has been shown to reduce antibody reactivity (Quintana et al. 2012).
- Any vaccinations received by mothers during the study will be recorded as concomitant medications.

Ocrelizumab—F. Hoffmann-La Roche Ltd

The B-cell subsets that will be analyzed are described in the table below.

Table 2B-Cell Subsets

- Naive B-cells: CD45+, CD19+, IgD+, CD27-, CD38dim/-
- Memory B-cells: CD45+, CD19+, CD27+
- Unswitched memory B-cells: CD45+, CD19+, IgD+, CD27+
- Switched memory B-cells: CD45+, CD19+, IgD-, CD27+
- Double-negative B-cells: CD45+, CD19+, IgD-, CD27-
- IgD transitional B-cells: CD45+, CD19+, IgD+, CD27-, CD38 bright
- Plasmablasts or plasma cells: CD45+, CD19+, CD27+, CD38 bright

